The purpose of this randomized controlled clinical trial is to compare the clinical success of a new formulation of a composite with an ultra-rapid polymerization time (F-Composite 2, Ivoclar Vivadent) to a commercially successful nanohybrid composite (Tetric EvoCeram, Ivoclar Vivadent, Buffalo, NY) and a previous formulation of the material ("Flash Composite", Ivoclar Vivadent) placed in Class I and Class II cavities in permanent teeth. The F-composite 2 material is a newly developed material from Ivoclar Vivadent. The objective of the study is to determine whether a simplified placement procedure of the F-composite 2 in a single increment of at most 4mm with a reduced amount of time of light polymerization (3 seconds) yields the same results as a widely used commercially available dental composite (Tetric EvoCeram). The new procedure would significantly facilitate and shorten the clinical procedure and potentially reduce voids between layers of composite. The restorations will be evaluated directly in the oral cavity at baseline (1

week), 6 months, 1 year, 2 years, and 3 years using modified FDI criteria. Casts made from impressions of the preparations will be analyzed to verify anatomic form and marginal integrity. Primary clinical outcome measures are frequency of post-operative hypersensitivity, pulp integrity, and the overall survival rate of the restorations in relation to the material. The secondary outcome measures of the study are surface luster, surface staining, color match, material fracture, occlusal wear, tooth integrity, caries, marginal adaptation, marginal staining, contact point, patient's satisfaction, and radiographic examination.

Ethical Standards

The study will be conducted in accordance with the Declaration of Helsinki (1964) as revised in Venice in 1983. Institutional Review Board approval has been obtained prior to commencing the study. Informed written consent will be obtained from all subjects prior to registration for participation in the evaluation. Implicit in giving informed written consent, each patient reserves the right to withdraw from the study at any time (See consent form).

Study Design

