The study will be a randomized, controlled clinical evaluation of class I and class II dental fillings in a single patient using one restorative materials: F-Composite 2 (Ivoclar Vivadent) placed with a dental adhesive Excite F (Ivoclar Vivadent) in a total-etch mode. This data will be compared to previously placed restorations in the first part of this study which compared two groups: Flash Composite (Ivoclar Vivadent) placed with a dental adhesive Excite F (Ivoclar Vivadent) in a total-etch mode and a commercially available dental composite, Tetric EvoCeram (Ivoclar Vivadent) placed with a dental adhesive Excite F (Ivoclar Vivadent) in a total-etch mode. One restoration will be placed in subjects with carious teeth or defective posterior restorations needing replacement. The study will be conducted in the Department of Clinical and Community Sciences, University of Alabama at Birmingham (UAB), School of Dentistry clinical research clinic. 60 restorations in adult subjects aged 19 years or older will be recruited into the study. Based on previous clinical trials, the average subject attrition rate at the three year recall is approximately 20%. To achieve 50 restorations per group at the three year recall, 60 restorations will be placed assuming a 20% drop out rate.

Investigators

[name] will act as the Principal Investigator and will conduct the calibration exercises. Four experienced operators will place the restorations in the study (Drs. [name], [name], [name], and [name]). All operators will place the same percentage of the restorations. One calibrated operator ([name]) will complete the baseline, 6 month, 1, 2, and 3 year recall examinations. Baseline evaluations will be conducted approximately one week after the restorations are placed.

Background and Significance

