One dental filling will be placed and evaluated in this study. The F-Composite 2, optimized for bulk placement (up to 4mm increments) and three second polymerization will be evaluated. It will be used with the bonding agent Adhese Universal (Ivoclar Vivadent) in a total-etch mode. All restored teeth will be in occlusion and at least one proximal surface of each class II restoration will be in contact with an adjacent tooth. Cavity preparations will be made the same way for all restorations following rubber dam isolation. A pre-operative photograph will be taken of all teeth in the study.

The experimental material will be cured with the prototype (Bluephase PowerCure) of a new curing device (3,400mW/cm²).

Data Analysis

The categorized clinical assessment (data see above) will be summarized by computing percentages for each category and used to describe any trends noted in the performance of the groups. In the analysis of categorical data of surface luster, surface staining, color match, material fracture, occlusal wear, tooth integrity, caries, marginal adaptation, marginal staining, contact point, post-operative hypersensitivity, patient's satisfaction, and radiographic examination, the frequency distribution over various categories will be calculated and reported. A sample size of 60 subjects is not based on a statistical plan, but rather on guidelines put forth by the American Dental Association.

APPENDIX 1
SCHEDULE OF EVENTS

Procedure	Screening	Preparation	Baseline	6 month	1 year	2 year	3 year
Preoperative radiograph	X						
Subject assignment #	X						
Preoperative sensitivity	X						
Preoperative photograph		X					
Photograph of cavity preparation		X					
Treatment		X					
Photograph	X	X	X	X	X	X	X
Direct Assessment							
Surface Luster			X	X	X	X	X
Surface Staining			X	X	X	X	X
Color Match			X	X	X	X	X
Material Fracture			X	X	X	X	X
Occlusal Wear			X	X	X	X	X
Tooth Integrity			X	X	X	X	X
Caries			X	X	X	X	X
Marginal Adaptation			X	X	X	X	X
Marginal Staining			X	X	X	X	X
Contact Point			X	X	X	X	X
Sensitivity			X	X	X	X	X
Patients View			X	X	X	X	X
Post-op Sensitivity			X	X	X	X	X
Radiographic examination	X					X	X
Indirect Assessment							
BW Radiograph	X					X	X
PA Radiograph (if necessary)			(X)	(X)	(X)	(X)	(X)
Complaints			X	X	X	X	X
Adverse events			X	X	X	X	X
Unanticipated Advers			X	X	X	X	X

Effects							
---------	--	--	--	--	--	--	--

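### The objective is a finding of sameness with Tetric EvoCeram, but Data Analysis plans no between-group difference or interval and does not name survival or pulp integrity, two of the three primary outcomes

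*Combined protocol and SAP*

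**What the plan says.** **Objective.** Study Objectives sets out to determine whether single-increment placement with a 3-second cure "yields the same results as a widely used commercially available dental composite (Tetric EvoCeram"). The same section states: "Primary clinical outcome measures are frequency of post-operative hypersensitivity, pulp integrity, and the overall survival rate of the restorations in relation to the material".

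**Comparison.** Study Design has new restorations placed in F-Composite 2 only. Of the Flash Composite and Tetric EvoCeram groups it says: "This data will be compared to previously placed restorations in the first part of this study which compared two groups".

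**Analysis.** Data Analysis has two sentences on method. The first is general: "The categorized clinical assessment (data see above) will be summarized by computing percentages for each category", and these are to be "used to describe any trends noted in the performance of the groups". The second lists 13 items, for which "the frequency distribution over various categories will be calculated and reported". Post-operative hypersensitivity is among them; survival and pulp integrity are not. Tooth integrity is listed, but Study Objectives treats it as a separate, secondary outcome.

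**Sample size.** Data Analysis adds: "A sample size of 60 subjects is not based on a statistical plan". No margin, alpha, power or expected event rate is given.

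**Assessments.** No row of Appendix 1 is named survival or pulp integrity. The sensitivity, radiograph, complaint and adverse-event rows may carry that information, but the text does not say so. Class of Restorations refers to Appendix 3 for the evaluation criteria, and Appendix 3 is not in the supplied text.

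**The concern.** The question is comparative and the planned output is not. Followed exactly, the plan yields side-by-side percentages for each material, with no estimate of the difference and no statement of its uncertainty. If the percentages look alike, the natural report is that the new procedure performs the same, although groups of this size may leave differences of several points, or more than ten, unexcluded.

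Survival and pulp integrity raise a second problem. Neither is named in the analysis, so the supplied text leaves open how they would be summarised, at which recall, and how replaced or lost restorations count. Those choices could then be made after the results are seen, against a comparator group that has already been treated.

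**Working it through.** **1. Outcomes against analysis**

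| Primary outcome (Study Objectives) | Named in Data Analysis? | Named row in Appendix 1? | Between-group estimate? |
|---|---|---|---|
| Post-operative hypersensitivity | Yes, as frequencies | Yes | None |
| Pulp integrity | No | No | None |
| Overall survival | No | No | None |

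**2. The plan's own numbers.** Study Design wants 50 restorations per group at three years, assumes 20% loss, and places 60. The 60 is reproduced by 50 × 1.20 = 60. Dividing by the retained fraction gives 50/0.80 = 62.5, so 63, and 60 placed with 20% loss leaves 60 × 0.80 = 48. That discrepancy is a separate matter. Here it only sets the range of group sizes: 48 (60 less 20%), 50 (the stated target) and 60 (no loss).

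**3. What an interval would show.** The documents give no failure counts and no size for the Tetric EvoCeram group, so these are assumed: equal groups, independent restorations, and the same number of failures x in each.

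With p = x/n and l, u the 95% Wilson limits for one group, the Newcombe half-width for the difference is √[(p − l)² + (u − p)²]. For x = 0 this reduces to u = 3.8415/(n + 3.8415).

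- n = 48, x = 0: 3.8415/51.8415 = 7.4 points.
- n = 48, x = 5: p = 10.42%, l = 4.53%, u = 22.17%; √(5.89² + 11.75²) = 13.1 points.

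| Failures per group | n = 48 | n = 50 | n = 60 |
|---|---|---|---|
| 0 | 7.4 | 7.1 | 6.0 |
| 2 | 10.3 | 9.9 | 8.4 |
| 5 | 13.1 | 12.7 | 10.8 |

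Every cell has an observed difference of zero. If instead 5 of 50 failed against 2 of 50, the difference would be 6.0 points with a 95% CI of −5.0 to 17.7.

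**4. Sensitivity to the unknown control size.** With no failures in either group and 48 F-Composite 2 restorations, the interval for the difference in failures (F-Composite 2 minus control) is −11.4 to +7.4 with 30 controls and −3.7 to +7.4 with 100.

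**5. Sensitivity to clustering.** The counts conflict. Study Design says: "One restoration will be placed in subjects with carious teeth or defective posterior restorations needing replacement". Data Analysis refers to 60 subjects. Distribution of Restorations allows two restorations per patient, and Patient Population gives fifty subjects.

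- With 60 subjects and one restoration each, there is no clustering.
- With 60 restorations in 50 subjects and at most two each, 40 subjects have one and 10 have two. Then Σm²/Σm = (40 + 40)/60 = 1.333, and the design effect is 1 + 0.333 × ICC. For an assumed ICC of 0.2 to 0.5 it is 1.067 to 1.167, and the effective n is 48/1.067 = 45.0 to 48/1.167 = 41.1. At the same failure rates and with both groups treated alike, the half-width becomes 10.7 to 11.4 points (2 failures) and 13.6 to 14.3 (5 failures).
- With no events an ICC cannot be estimated from the data. Counting patients gives 50 × 0.80 = 40 per group and 3.8415/43.8415 = 8.8 points, against 7.4 for 48 restorations.

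**The case against.** **The plan is openly descriptive.** It disclaims a statistical basis for its sample size and states no hypothesis, margin or alpha, and its primary outcomes are themselves phrased as frequencies and rates. A descriptive analysis is defensible in a study of this size. What does not follow is a conclusion of sameness; a descriptive study needs a descriptive objective. A reader with the counts could compute an interval, but the plan does not commit anyone to doing so.

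**The general sentence may already cover the missing outcomes.** The first sentence of Data Analysis is broad enough that survival and pulp status might fall under it. This stands in part: one cannot say they are deliberately excluded, only that they are not named.

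**Events may be defined elsewhere.** A reader might infer that the plan never defines failure or loss of pulp integrity. The documents do not support that inference, because the criteria are referred to Appendix 3, which is not available here. Scoring criteria would still not supply an analysis or a between-group estimate.

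**An interval leaves the larger weakness untouched.** The comparator is not concurrent, and the documents disagree on the adhesive for F-Composite 2: Study Design names Excite F, Materials and Methods names Adhese Universal. This stands. A sampling interval covers neither problem, and the report should say so.

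**Conclusion.** The point holds in this form: the stated methods cannot support the stated conclusion, and two of the three primary outcomes have no named analysis. It should be corrected before the data are analysed.

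The textual finding depends on no assumption. Its size is illustrative only: with identical observed results, about 6 to 7 points either way with no failures and 11 to 13 points with five per group, for equal groups of 48 to 60 independent restorations. Control size, failure counts and correlation are assumed throughout. A different control size changes the interval, but within the range tried it never becomes narrow enough for matching percentages to speak for themselves.

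A reader might also infer that no comparison is intended, or that the sponsor claims formal equivalence. Neither is supported. A comparison with the first part is announced but given no method beyond describing trends, and the sameness wording comes with no margin or test.

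**What to change.** In Data Analysis:

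- **(a) Outcomes.** Name survival and pulp integrity as analysed outcomes. Define failure and loss of pulp integrity from assessments already scheduled, or cross-refer to Appendix 3 if they are defined there. Name the recall at which hypersensitivity is compared.
- **(b) Per-group estimates.** Report 3-year survival and cumulative loss of pulp integrity with 95% CIs. Carry earlier failures forward, state how a restoration replaced for another reason counts towards pulp integrity, and show the number with unknown status. If Kaplan-Meier is used, choose limits that do not collapse to zero width when there are no events.
- **(c) Difference.** For each primary outcome give F-Composite 2 minus Tetric EvoCeram with a 95% Newcombe or exact CI, from first-part restoration-level data if available and otherwise from its group counts. Reconcile the subject and restoration counts in Study Design, Distribution of Restorations, Patient Population and Data Analysis. If any patient has two restorations, allow for clustering, and count patients when there are no events.
- **(d) Conclusion.** Replace the sameness wording in Study Objectives with the estimated difference and its CI. State that the control is non-concurrent, that the CI covers sampling error only, and that equivalence is not claimed. Reconcile the adhesive named in Study Design with that in Materials and Methods, because it affects whether the contrast isolates the composite.

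**Cost.** Definition work, modest programming and a request for first-part data, whose availability the documents do not establish; no added visits. Definitions built from existing assessments may capture pulp loss imperfectly. Counting patients widens the interval slightly (8.8 against 7.4 points in the zero-event example), and the claim of sameness becomes visibly weaker.

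### Pre-operative sensitivity is recorded at screening but not used in Data Analysis, so sensitivity that persists from before treatment can count against the restoration on a primary outcome

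*Combined protocol and SAP*

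**What the plan says.** - **Outcome.** Study Objectives states: "Primary clinical outcome measures are frequency of post-operative hypersensitivity, pulp integrity, and the overall survival rate of the restorations".
- **Pre-operative record.** The Schedule of Events in Appendix 1 has a row "Preoperative sensitivity", marked once, at screening. The variable is not mentioned in the outcomes, the eligibility criteria or Data Analysis.
- **Post-operative record.** The same table has a row "Post-op Sensitivity" at baseline (about one week), 6 months, 1, 2 and 3 years. A second row, headed simply sensitivity, is marked at the same five visits. The difference between the two rows is not explained.
- **Analysis.** For a list of variables that includes post-operative hypersensitivity, Data Analysis says "the frequency distribution over various categories will be calculated and reported". The categorised assessments "will be summarized by computing percentages for each category and used to describe any trends noted in the performance of the groups".
- **Eligible teeth.** Study Design says "One restoration will be placed in subjects with carious teeth or defective posterior restorations needing replacement". The Exclusion Criteria remove non-vital teeth, teeth with signs of pulpal pathology and teeth whose pulp is exposed during preparation. Sensitivity as such is not an exclusion.
- **Comparator.** Study Design says of the new material's results: "This data will be compared to previously placed restorations in the first part of this study".
- **Scoring.** Class of Restorations places the evaluation criteria in Appendix 3, which is not in the text available here.

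**The concern.** Carious teeth and teeth with failing restorations may be sensitive before anything is done to them. If such a tooth is still sensitive at a recall visit, a crude frequency does not distinguish it from a tooth that became sensitive after the filling. Only the second case is informative about the material and its placement.

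Within one cohort, this inflates the apparent rate. Between cohorts it can do more harm. The new material is set beside restorations placed earlier, so concurrent randomisation does not balance pre-operative sensitivity between the new group and the part-one groups. A cohort that entered with more sensitive teeth could show more post-operative hypersensitivity even if the materials behaved identically. The trial's aim is to learn whether a simplified placement with short curing gives the same results as an established composite, so a false difference on a primary outcome bears directly on its conclusion. The variable needed to examine this is already scheduled for the new cohort.

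**Working it through.** **The plan's own figure.** There is none to reproduce. The documents give no sensitivity rate, before or after treatment, so every rate below is an assumption.

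**Between cohorts.** Let p be the proportion of teeth sensitive before treatment, r1 the post-operative rate in those teeth, and r0 the rate in the others. Suppose the material has no effect, so r1 and r0 are the same in both cohorts.

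Crude rate = p × r1 + (1 − p) × r0

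False difference = (pA − pB) × (r1 − r0)

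With r0 = 5% throughout:

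| Assumed r1 | p in the two cohorts | Crude rates | False difference |
|---|---|---|---|
| 30% | 20% vs 40% | 0.06 + 0.04 = 10%; 0.12 + 0.03 = 15% | 5 points |
| 20% | 20% vs 40% | 0.04 + 0.04 = 8%; 0.08 + 0.03 = 11% | 3 points |
| 30% | 30% vs 35% | 12.5%; 13.75% | 0.05 × 0.25 = 1.25 points |
| 20% | 30% vs 35% | 9.5%; 10.25% | 0.05 × 0.15 = 0.75 points |

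If p is equal in the two cohorts, the false difference is zero.

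**Cross-check by persistence.** Let c = prevalence × persistence be the share of teeth carrying sensitivity over, with a new-onset rate of 5% in the rest.

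Observed rate = c + (1 − c) × 0.05

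With 25% persistence and prevalence of 30% vs 10%, c is 0.075 vs 0.025. The observed rates are 12.125% vs 7.375%, a false difference of 4.75 points.

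**Within one cohort.** The same formula, with prevalence of 10% to 40% and persistence of 10% to 50%, gives c from 0.01 to 0.20. That is 0.6 to 12 of 60 restorations. The observed rate would be between 0.01 + 0.99 × 0.05 = 6.0% and 0.20 + 0.80 × 0.05 = 24.0%, where new onset alone is 5%.

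**Scale.** One restoration in 60 is 1.7 points. A 5-point artefact is 0.05 × 60 = 3 restorations. The 0.75 to 1.25 point case is less than one.

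**The case against.** A reader might infer that any sensitivity present before treatment counts against the restoration, or that the primary outcome is bound to mix old and new sensitivity. The documents do not support either reading.

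- Sensitivity that resolves is not counted at recall. Only sensitivity that persists can be.
- The scoring criteria are in Appendix 3. They may define post-operative hypersensitivity as new, or relative to the pre-operative state, and their absence here is not a fault of the plan. The two separate follow-up rows might likewise divide general from treatment-related sensitivity, although nothing in the text says so.
- The pulpal exclusions plausibly remove some of the teeth most likely to have lasting symptoms. A vital tooth that is sensitive but shows no sign of pulpal pathology can still enter.

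These three points stand, and the conclusion is limited accordingly.

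The size can also be challenged. The 5-point case needs a two-fold imbalance in prevalence and a six-fold risk ratio (30% against 5%). Assuming 60 per group (the part-one group sizes are not stated), the standard error of a 10% vs 15% difference is √(0.10 × 0.90/60 + 0.15 × 0.85/60), about 6 points, so even that artefact lies within sampling noise. The plan is descriptive and has no test for the bias to push to significance. This is fair as to scale. But percentages used to describe trends between groups can mislead without a test, and sampling noise does not excuse a bias that collected data could reveal.

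Finally, the non-concurrent comparator is the deeper problem, and pre-operative sensitivity is only one factor that may differ. That is correct. Stratifying on it would not make the comparison a randomised one.

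**Conclusion.** The point holds in a limited form. A baseline value directly relevant to a primary outcome is collected, and Data Analysis does not say how it will be used. As that section is written, persisting pre-operative sensitivity can count against the restoration, and a difference between cohorts in pre-operative sensitivity could appear as a difference between materials. This is conditional on Appendix 3 not already scoring the outcome relative to the pre-operative state.

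The size is unknown. Under the assumed values the false difference is about 1 point for a slight imbalance and up to 5 points for a large one, and it vanishes if the cohorts entered with equal prevalence. The plan should be amended because the repair is nearly free, not because a large bias has been shown. The argument does not require the primary outcome to be redefined as new or worsened sensitivity. That is a debatable choice, and showing it beside the crude frequency is enough.

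**What to change.** In Data Analysis:

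1. Report post-operative hypersensitivity at each visit cross-tabulated by pre-operative status. Show new or worsened sensitivity separately from persisting sensitivity, and keep the crude frequency alongside.
2. Present the comparison with the part-one groups stratified by pre-operative status where part one recorded it. Where it did not, label the comparison unadjusted.
3. If Appendix 3 already scores the outcome relative to the pre-operative state, cite that rule. State which of the two follow-up sensitivity rows supplies the primary outcome.

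The cost is some wording, one extra table and a check of part-one records. No new data are needed for the new cohort, and the sample size does not change. With few events the stratum estimates will be imprecise: at the crude rates of 10% and 15% above, a group of 60 has only 6 to 9 events. Other differences between the non-concurrent cohorts remain.

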- Have xerostomia either by taking medications known to produce xerostomia or those with radiation induced or Sjögren's syndrome subjects since dry mouth increases tooth and restoration wear as well as the development of caries.
- Have teeth with advanced or severe periodontitis or rampant caries or poor oral hygiene which may require extraction of the teeth to be restored
- Present with any systemic or local disorders that contra-indicate the dental procedures included in this study
- Have an unstable occlusion
- Have severe bruxing or clenching or need of TMJ related therapy
- Have tooth with exposed pulp during preparation or caries removal
- Teeth that are non-vital or that exhibit signs of pulpal pathology for restoration
- Teeth that require cuspal build-ups involving more than one cusp

Screening

Each subject will be screened for compliance with the inclusion/exclusion criteria specified above. Subjects will be given the consent form and after careful reading any questions will be answered. We will additionally explain any terms, phases or descriptors the subject may not understand. After signing the consent form they will receive a copy of the form.

Risks to the Patient

Subjects will wear lead aprons as a protective measure during the radiographic procedure to minimize risk. Patient data will be monitored and if, during the course of the study, it becomes apparent that any restorative material has poor performance the patient will be informed and if needed the restorations replaced without any costs for the patient.

Consent

Consent for this study will be obtained prior to the initial examination and the initiation of any portion of the study. The PI or Co-investigator will explain the consent to the patient and answer questions they have. The consent forms and all records associated with this study will be maintained in the clinical research office (Room 610) under lock to ensure the records are confidential. Each subject will provide written consent to participate in this study in accordance with Federal regulations (21 CFR Parts 50 and 56).

Materials and Methods

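### Appendix 1 schedules no safety collection at the Preparation visit, where all treatment is given; the first is at Baseline, about a week later, with no stated look-back

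*Combined protocol and SAP*

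**What the plan says.** The visit columns of the Schedule of Events (Appendix 1) are "Procedure Screening Preparation Baseline 6 month 1 year 2 year 3 year". Treatment carries a single mark, under Preparation. The three safety rows are "Complaints X X X X X", "Adverse events X X X X X" and "Unanticipated Advers X X X X X" (the last label is broken across lines and continues with the word Effects). In each, the five marks fall at Baseline, 6 months and 1, 2 and 3 years.

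On timing, the Investigators section states: "Baseline evaluations will be conducted approximately one week after the restorations are placed". Study Objectives also gives one week for Baseline. On exposure, Materials and Methods states: "The experimental material will be cured with the prototype (Bluephase PowerCure) of a new curing device", and gives its output as 3,400 mW/cm².

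The Exclusion Criteria include an event that can arise only once work on the tooth has begun: "Have tooth with exposed pulp during preparation or caries removal". By then the patient has consented (Consent section) and has a subject number, which Appendix 1 assigns at Screening.

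The only other safety text supplied is in Risks to the Patient. It provides for lead aprons during radiography and for general monitoring in case a restorative material performs badly. It sets no period for adverse event collection and does not ask for events during treatment to be recorded.

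**The concern.** What is new in this trial is used at one visit: a newly developed composite, cured in three seconds with a prototype light. An immediate reaction to the material, discomfort during curing or a device fault would occur at that visit. The exclusion of patients with a known monomer allergy shows that the protocol regards at least one such hazard as real. These are examples of what could occur; the documents give no rate for any of them.

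A site that follows the schedule as written is not prompted to record anything of this kind on the day. A short-lived event then enters the data only if the patient, or someone else, brings it up about a week later. A low count of acute events would be hard to interpret, because it could reflect either few events or poor recall.

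There is a second gap. A patient excluded in the chair has been consented and numbered, but the schedule holds no safety entry for that visit. Without one, the number of such patients and the reasons for their exclusion may not be reported.

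**Working it through.** No sample size, power or event-rate figure enters this point. The check is a reading of the table against the text.

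1. **Is the grid intact?** The header has 8 fields: the procedure label and 7 visits. The general photograph row, "Photograph X X X X X X X", fills all 7 visits, Preparation included. The rows for the preoperative photograph, the photograph of the cavity preparation and Treatment each fall in the Preparation column. The blanks in the safety rows are therefore unlikely to come from the PDF reading.

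2. **Where do the marks fall?**

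| Row | Screening | Preparation | Baseline to 3 years |
|---|---|---|---|
| Treatment | blank | X | blank |
| Complaints | blank | blank | X at all 5 |
| Adverse events | blank | blank | X at all 5 |
| Unanticipated adverse effects | blank | blank | X at all 5 |

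 The three safety rows have 3 × 7 = 21 cells, of which 3 × 5 = 15 are marked. The 6 blanks are Screening and Preparation in each row. At Preparation, 0 of 3 are marked.

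3. **How long is the gap?** From treatment (Preparation) to the first scheduled collection (Baseline) is about one week.

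4. **How many treatments does it cover?** All 60 planned restorations are placed at a Preparation visit, so all 60. I count restorations because the number of subjects is inconsistent: 50 in Patient Population, 60 in Data Analysis.

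5. **Who records at Baseline?** Four operators place equal shares, 60 / 4 = 15 restorations each, and one calibrated operator does every follow-up examination. Names are removed, so it cannot be seen whether that person is one of the four. If so, 60 − 15 = 45 restorations are examined at Baseline by someone who did not place them; if not, all 60 are.

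6. **Does other text close the gap?** I looked for a defined adverse event period, an instruction to record events during treatment, and a statement that Baseline covers the time since placement. The supplied text has none of these. Photographs are scheduled at Preparation, but they are not a safety record.

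**The case against.** The strongest reply is that a mark in a schedule shows when a question is asked, not the period it covers. The 6-month and 1-year marks would ordinarily cover the time since the previous visit, and Baseline can be read the same way, back to placement. This stands in part. A reader might infer from the blank cells that nothing from the treatment day will be recorded, and the documents do not support that: recall at Baseline is possible, as is a note in the dental chart. They require neither, however, and a week's recall is a weaker source than an entry made on the day.

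The second reply concerns pulp exposure, and it is right. An exposed tooth is excluded before filling and curing, so it receives neither the new composite nor the prototype light. It is a procedural event and says nothing about the safety of the material or the device. Nor is the patient necessarily lost, since Distribution of Restorations allows a second restoration. What remains is that the visit itself carries no scheduled entry for that patient.

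Third, the supplied file is incomplete: some pages were removed, and Appendix 3, which the protocol cites, is not among the text. Silence there proves nothing. But the point rests on a schedule that is present and explicit, not on silence alone.

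Fourth, the primary outcomes of post-operative hypersensitivity and pulp integrity are assessed after placement, and post-operative sensitivity is marked from Baseline on. That is correct, and it limits the consequence.

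**Conclusion.** The point holds in limited form. The schedule has no safety collection at the one visit where all treatment is given; the first comes about a week later without a stated look-back. It touches all 60 planned restorations, plus an unknown number of patients excluded during preparation.

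The consequence is confined to acute events, which are captured at best by recall. The three-year restoration outcomes are unaffected. No numerical bound on an event rate is offered: the documents state no expected rate or target, the unit of analysis is unsettled, and a bound on a hypothetical result would not measure this defect.

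A reader might go further and conclude that the trial would miss device-related events altogether, or that patients excluded in the chair vanish from the data. Neither follows from the documents.

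The verdict assumes that the table was read from the PDF with its columns in place, which the fully marked photograph row supports, and that no removed or unsupplied page defines an earlier start of collection.

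**What to change.** - In Appendix 1, mark Complaints, Adverse events and Unanticipated Adverse Effects under Preparation.
- Add a sentence stating that collection runs from the start of the Preparation visit and includes patients excluded during it, who are reported separately with the reason for exclusion.
- State that the operator who treats the patient completes the entry before the patient leaves.
- State that the Baseline entry covers the time since the Preparation visit, so that the two entries meet without a gap.

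The cost is three marks, a few lines of protocol text and one short form at an existing visit. No visit, procedure or staff member is added, and no rule of clinical management changes. The downside is the operator's time for the form and a reported event count that may be slightly higher.
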